3. STUDY DESIGN

3.1. Study Design

This is an open-label, multicenter, single-arm study to assess the safety, tolerability, pharmacokinetics, and efficacy of E/C/F/TAF FDC in HIV-1 infected adult subjects with ESRD on chronic HD.

Approximately 50 subjects with ESRD on chronic HD will be enrolled. All subjects will switch from their current antiretroviral regimen to E/C/F/TAF on Day 1. The total treatment duration will be at least 96 weeks. After at least 96 weeks, subjects will be given the option to roll into an OL extension of B/F/TAF FDC for at least 48 weeks.

Figure 3-1. Study Schema

- a Following the Day 1 Visit, subjects will return for study visits at Weeks 2, 4, 8, 12, 24, 36, 48, 60, 72, 84, and 96.
- b After Week 96, subjects in the US will continue to take their study drug and attend visits every 12 weeks until the End of E/C/F/TAF Visit. At Week 96 or the End of E/C/F/TAF Visit, subjects will discontinue E/C/F/TAF FDC and be given the option to receive OL B/F/TAF FDC. All subjects participating in the OL rollover extension of B/F/TAF FDC will return for study visits at Week 4 OL, Week 12 OL, and every 12 weeks thereafter for at least 48 weeks.
- c Subjects who discontinue study drug administration before their Week 96 Visit will complete an ESDD Visit. These subjects may remain on the study off study drug up to the Week 96 Visit. Subjects participating in the OL rollover extension of B/F/TAF FDC who discontinue study drug prematurely will complete an ESDD Visit.
- d Subjects who complete the study through the Week 96 Visit and do not continue on the OL rollover extension of B/F/TAF FDC will be required to return to the clinic after the Week 96 visit for a 30 Day Follow-Up Visit.

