6.3. Treatment Assessments (Weeks 2-96)

All study visits are to be scheduled relative to the Day 1 Visit date. Study visits are to be completed within \pm 2 days of the protocol-specific visit date through Week 12 and completed within \pm 6 days of the protocol-specific visit date through Week 36. The visit window at Week 48 will be \pm 6 weeks of the protocol-specific visit date, and this clinical visit window coincides with the Week 48 statistical analysis window for HIV-1 RNA. Unless notified by the Sponsor, Week 48 visit should be completed within \pm 6 days of the protocol-specific visit date. Following the Week 48 Visit, study visits are to be completed within \pm 6 days of the protocol-specific visit date through Week 84. The visit window at Week 96 will be \pm 6 weeks of the protocol-specific visit date. Unless notified by the Sponsor, Week 96 visit should be completed within \pm 6 days of the protocol-specific visit date.

The following evaluations are to be completed at the end of Weeks 2, 4, 8, 12, 24, 36, 48, 60, 72, 84, and 96, unless otherwise specified.

Note: Regularly scheduled evaluations will be made on all subjects whether or not they continue to receive study drug.

- Pre-dose (within 30 minutes prior to study drug administration) whole blood samples collection for plasma and PBMC samples (**Week 4 or Week 12 only**).

Note: Week 4 or Week 12 Visit should occur on the day of hemodialysis for this sample collection. Study drug administration should occur after completion of hemodialysis and should be observed on-site.

- PBMC sample processing will be performed by the central laboratory and plasma sample processing will be performed on-site. Details of the blood sampling procedures and sample management will be documented in the central laboratory manual.

- CCI
[REDACTED]
 - CCI
[REDACTED]
 - Review of AEs and changes in concomitant medications
 - Complete physical examination (**Weeks 24, 48, and 96 only**) (urogenital/anorectal exams will be performed at the discretion of the Investigator)
 - Symptom-directed physical examination as needed (**Weeks 2, 4, 8, 12, 36, 60, 72, and 84**)
 - Vital signs (blood pressure, pulse, respiration rate, and temperature) and weight
 - 12-lead ECG performed supine (**Weeks 48 and 96**)
 - Blood sample collection for the following laboratory analyses:

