6.5. Post-treatment Assessments

6.5.1. 30-Day Follow-up Assessments

Those subjects who prematurely discontinue study drug and continue in the study through at least one subsequent visit after the Early Study Drug Discontinuation Visit will not be required to complete the 30-Day Follow-Up Visit.

Subjects who prematurely discontinue study drug and refuse to continue in the study through the End of E/C/F/TAF Visit will be asked to return to the clinic 30 days after the completion of the ESDD Visit for the 30-Day Follow-Up Visit.

Subjects who complete the study through the End of E/C/F/TAF Visit and do not continue on the B/F/TAF OL rollover extension will be required to return to the clinic after the End of E/C/F/TAF visit for a 30 Day Follow-Up Visit.

Subjects who prematurely discontinue study drug during the Open-Label rollover extension will be asked to return to the clinic 30 days after the completion of the ESDD Visit for the 30-day Follow-Up Visit. The subject will not continue attending the scheduled study visits.

Subjects who complete the Open-Label rollover extension will be asked to return to the clinic 30 days after the completion of study drug for the 30-day Follow-Up Visit.

For the purpose of scheduling a 30-Day Follow-Up Visit, a \pm 6 days window may be used. The following evaluations are to be completed at the 30-Day Follow-Up Visit:

- Review of AEs and changes in concomitant medications
- Symptom-directed physical examination as needed
- Weight
- Blood sample collection for the following laboratory analyses:
 - Chemistry profile: alkaline phosphatase, AST, ALT, total bilirubin, direct and indirect bilirubin, total protein, albumin, CPK, bicarbonate, BUN, calcium, chloride, creatinine, glucose, phosphorus, magnesium, potassium, sodium, uric acid, amylase (reflex lipase testing is performed in subjects with total amylase $> 1.5 \times$ ULN) and PTH.
 - Sample should be drawn prior to hemodialysis
 - Timing of draw and timing of hemodialysis should be recorded
 - Hematology profile: CBC with differential and platelet count
 - Plasma HIV-1 RNA (Taqman v2.0)
 - CD4+ T cell count
 - Serum pregnancy test (females of childbearing potential only)
 - Serum and plasma storage samples for possible additional clinical testing (for subjects who provide consent)

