3.8. Analysis Windows

3.8.1. Definition of Study Day

Study Day 1 is defined as the day when the first dose of E/C/F/TAF study drug was taken, as recorded on the Study Drug Administration eCRF form.

B/F/TAF Study Day 1 is defined as the day when the first dose of B/F/TAF study drug was taken, as recorded on the Study Drug Administration eCRF form.

Study Days are calculated relative to Study Day 1 and B/F/TAF Study Day 1. For events that occurred on or after Study Day 1, study days are calculated as (visit date minus Study Day 1 plus 1). For events that occurred prior to Study Day 1, study days are calculated as (visit date minus Study Day 1).

E/C/F/TAF Last Dose Date is the latest of E/C/F/TAF study drug end dates recorded on the Study Drug Administration eCRF form with “Permanently Withdrawn” box checked for subjects who prematurely discontinued study drug or who completed study drug according to the Study Drug Completion eCRF.

If the date of E/C/F/TAF last dose is missing (eg, only year of last dose is known or completely missing due to lost to follow-up) for subjects who prematurely discontinued or completed study drug, the latest of the E/C/F/TAF study drug start dates and end dates, the clinic visit dates, and the laboratory visit dates, excluding the date of the 30-day follow-up visit and any dates on or after the first dose of B/F/TAF if applicable, will be used to impute the last dose date. For other partial missing last dose dates, please see programming specifications ([Appendix 7](#)) for imputation rule details.

B/F/TAF Last Dose Date is the latest of B/F/TAF study drug end dates recorded on the Study Drug Administration eCRF form with “Permanently Withdrawn” box checked for subjects who prematurely discontinued study drug or who completed study drug according to the Study Drug Completion eCRF.

If the date of B/F/TAF last dose is missing (eg, only year of last dose is known or completely missing due to lost to follow-up) for subjects who prematurely discontinued or completed study drug, the latest of the B/F/TAF study drug start dates and end dates, the clinic visit dates, and the laboratory visit dates, excluding the date of the 30-day follow-up visit and any dates before the first dose of B/F/TAF, will be used to impute the last dose date. For other partial missing last dose dates, please see programming specifications ([Appendix 7](#)) for imputation rule details.

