Appendix Table 6. ARV Category

Pre-ARV Categories	CMTRT3	ABBR	INGRED
TDF containing ARV	NRTI/INI: Stribild (EVG+COBI+FTC+TDF)	STB	EVG COBI FTC TDF
	NRTI/NNRTI: Atripla (EFV+FTC+TDF)	ATR	EFV FTC TDF
	NRTI/NNRTI: Complera (FTC+RPV+TDF)	CPA	FTC RPV TDF
	NRTI: Tenofovir DF (TDF)	TDF	TDF
	NRTI: Truvada (FTC+TDF)	TVD	FTC TDF
COBI/RTV/RPV containing ARV	NRTI/INI: Stribild (EVG+COBI+FTC+TDF)	STB	EVG COBI FTC TDF
	NRTI/NNRTI: Complera (FTC+RPV+TDF)	CPA	FTC RPV TDF
	NNRTI: Rilpivirine (RPV)	RPV	RPV
	PI: Kaletra (LPV+RTV)	LPV/r	LPV RTV
	PI: Ritonavir (RTV)	RTV	RTV
	Other	COBI	COBI
ABC containing ARV	NRTI: Abacavir (ABC)	ABC	ABC
	NRTI: Epzicom/Kivexa (ABC+3TC)	EPZ	ABC 3TC
	NRTI: Trizivir (ABC+AZT+3TC)	TZV	ABC AZT 3TC
FTC containing ARV	NRTI/INI: Stribild (EVG+COBI+FTC+TDF)	STB	EVG COBI FTC TDF
	NRTI/INI: Genvoya (EVG+COBI+FTC+TAF)	E-C-F-TAF	EVG COBI FTC TAF
	NRTI/NNRTI: Atripla (EFV+FTC+TDF)	ATR	EFV FTC TDF
	NRTI/NNRTI: Complera (FTC+RPV+TDF)	CPA	FTC RPV TDF
	NRTI: Emtricitabine (FTC)	FTC	FTC
	NRTI: Truvada (FTC+TDF)	TVD	FTC TDF
3TC containing ARV	NRTI: Lamivudine (3TC)	3TC	3TC
	NRTI: Epzicom/Kivexa (ABC+3TC)	EPZ	ABC 3TC
	NRTI: Trizivir (ABC+AZT+3TC)	TZV	ABC AZT 3TC
	NRTI: Combivir (AZT+3TC)	CBV	AZT 3TC
FTC containing ARV	NRTI/INI: Stribild (EVG+COBI+FTC+TDF)	STB	EVG COBI FTC TDF

13) Last Dose Dates and Last Study Date:

- a) Last Dose Date is defined in SAP Section 3.8.1. If the last dose date is incomplete or missing, the last dose date will be imputed as follows, using E/C/F/TAF or B/F/TAF dosing information as appropriate:
 - If the last dose date is missing day (ie, month and year of the last dose are known), the latest of dispensing dates of study drug bottles, study drug start dates and end dates, and imputed last dose date (day imputed as 15) will be used to impute the last dose date. However, if the month of the dispensing date is after the month of the last dose date, data query is needed. If subject died and the death date is complete (ie, not partial date) and before the imputed last dose date, the complete death date should be used as the imputed last dose date.
 - If the last dose date is missing day and month or completely missing (eg, due to lost to follow-up), the latest of study drug start dates and end dates, clinical visit dates, and laboratory visit dates (excluding the date of 30-day follow-up visit date) will be used to impute the last dose date.

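### When the E/C/F/TAF last dose date is known only to the year or not at all, the SAP's imputation rule can place it at an off-drug visit, because nothing limits it to the early discontinuation visit

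*SAP*

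**What the plan says.** SAP 3.8.1 covers subjects who discontinued or completed E/C/F/TAF and whose last dose date is largely unknown; its example is "only year of last dose is known or completely missing due to lost to follow-up". The imputed date is the latest of the drug start and end dates, "the clinic visit dates, and the laboratory visit dates, excluding the date of the 30-day follow-up visit". Dates on or after first B/F/TAF dose are also excluded.

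Appendix 7 item 13 gives the same rule for programming. If the date is "missing day and month or completely missing (eg, due to lost to follow-up), the latest of study drug start dates and end dates" is compared with the visits: "clinical visit dates, and laboratory visit dates (excluding the date of 30-day follow-up visit date) will be used to impute the last dose date". If only the day is missing, item 13 does not use visits. It compares dispensing dates and drug dates with an "imputed last dose date (day imputed as 15) will be used to impute the last dose date", and a complete death date caps the result.

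The protocol separates attendance from dosing. On subjects who stop before Week 96, Section 3.1 (Figure 3-1, note c) says: "These subjects may remain on the study off study drug up to the Week 96 Visit". Section 6.3 says: "Regularly scheduled evaluations will be made on all subjects whether or not they continue to receive study drug". Section 6.5.2 asks for an ESDD visit within 72 hours of stopping and for continued attendance through Week 96. Under Section 6.5.1, subjects seen at least once after ESDD "will not be required to complete the 30-Day Follow-Up Visit".

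**The concern.** A rule that takes the last visit as the last dose assumes that a subject who attends is still on drug. This protocol deliberately breaks that link up to Week 96.

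Neither exclusion in the rule protects the subjects at risk. The 30-day visit is one they need not have. The B/F/TAF exclusion does not reach them either, because Protocol 6.4.2 and 6.5.2 bar subjects who stopped early from the extension. For a retained subject without a 30-day visit, the imputed last dose date is the same as the Last Study Date, which SAP 3.8.1 builds from the same list of dates plus that visit.

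The last dose date feeds several analyses:
- exposure and the Kaplan-Meier time to premature discontinuation (SAP 4.2.1);
- the on-treatment limit of the Week 96 snapshot, set at last dose plus 1 day (7.2.1);
- on-treatment CD4 values (7.2.2.2);
- the 30-day windows for adverse events (8.3.5.1) and laboratory abnormalities (8.4.2.1).

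Where the rule misfires, it lengthens apparent persistence on drug and can raise the apparent response.

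**Working it through.** **Inputs.** The analysis set has 55 subjects (SAP Appendix Table 1). The Week 96 window is Day 631 to 714, and its nominal day is 672 (SAP 7.2.1, Table 3-1). The Week 48 results come from Protocol 1.2.5. The documents do not say how many last dose dates are this incomplete, so k = 0 to 3 below is an assumption.

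**1. Reproduce the reported figure.** The snapshot at Week 48 is 81.8% (69.1% to 90.9%). 45/55 = 81.8%, and the exact (Clopper-Pearson) interval is 69.1% to 90.9%, so it agrees.

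**2. Apply the rule.** Suppose the last dose date is wholly missing and the subject attends the Week 96 visit on Day 672. The imputed last dose is Day 672. Excess exposure in weeks = (672 − true stop day)/7.

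| True stop | Stop day | Excess exposure | 30-day window should end | Window ends under the rule |
|---|---|---|---|---|
| Week 12 | 84 | 84 weeks | Day 114 | Day 702 |
| Week 24 | 168 | 72 weeks | Day 198 | Day 702 |
| Week 48 | 336 | 48 weeks | Day 366 | Day 702 |
| Week 72 | 504 | 24 weeks | Day 534 | Day 702 |

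In every row the Day 672 HIV-1 RNA lies in the Week 96 window and, because 672 ≤ 672 + 1, is treated as on-treatment. A value below 50 copies/mL then counts as success. With the true stop day, no on-treatment value lies in the window. The subject would be classed as having no virologic data or, if the last on-treatment value was ≥ 50 copies/mL or the drug was stopped for lack of efficacy, as ≥ 50 copies/mL.

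**3. Limit the date to the ESDD visit.** For the Week 24 stop, ESDD within 72 hours puts the last dose between Day 168 and Day 171. Exposure is then about 24 weeks and the 30-day window ends between Day 198 and Day 201. The Day 672 value is off-treatment, as it should be.

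**4. Size in the summaries.** Each affected subject moves the snapshot by 1/55 = 1.8 points. A Week 24 stop moves mean exposure by 72/55 = 1.3 weeks. The Week 96 count is not in the documents; on an illustrative base of 45/55:

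| k | Snapshot < 50 copies/mL | Exact 95% CI |
|---|---|---|
| 0 | 81.8% | 69.1% to 90.9% |
| 1 | 83.6% | 71.2% to 92.2% |
| 2 | 85.5% | 73.3% to 93.5% |
| 3 | 87.3% | 75.5% to 94.7% |

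**5. Is there off-drug HIV-1 RNA at all?** At Week 48, missing-equals-failure gave 83.6% = 46/55 and missing-equals-excluded gave 97.9% = 46/47, against 45 snapshot successes. If the first two used every in-window value, at least one suppressed value existed that the snapshot did not count. This is an inference, since the Week 48 SAP is not among the documents. It suggests that such values occur but are few.

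**The case against.** The strongest reply is that the trigger is rare. The date must lack both day and month, and the subject must keep attending. The SAP's own example is loss to follow-up, where there are usually no later visits and the last visit is a fair proxy. Subjects who stay are the easiest to date. They are due an ESDD visit with drug accountability (Protocol 6.5.2), source records must hold drug end dates (9.1.5), and discrepancies are queried (9.1.6). The Week 12 example needs seven further scheduled visits (Weeks 24 to 96) at which nobody establishes even the month of stopping. Attendance is also requested, not guaranteed. All of this stands, and it limits how often the error can occur. It does not make the rule right when it is triggered.

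Three stronger readings are tempting, and the documents do not support them:
- A reader might infer that all later adverse events would become treatment-emergent. Protocol 7.3.1 collects routine events only to 4 weeks after last dose. Serious events are reported throughout the study (7.3.2), so the effect falls mainly on those and on laboratory data.
- A reader might infer that retained subjects never have a 30-day visit. Section 6.5.1 says only that it is not required.
- A reader might infer that every subject who stops is given a new regimen within the study. The text on configuring one (Figure 6-1 notes) concerns virologic failure.

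**Conclusion.** The concern holds as a conditional fault in a stated rule. When a last E/C/F/TAF dose date lacks at least day and month and the subject attended after stopping, the SAP can date the last dose to an off-drug visit, and no other text prevents it. Exposure would be overstated by 24 to 84 weeks in the cases worked, and the Week 96 snapshot could rise by 1.8 points per subject.

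It does not follow that off-drug time has actually been counted as treatment. The number affected is unknown and is probably small or zero. The primary endpoint was analysed for the Week 48 report and is not repeated under this SAP (Section 6.1). The by-visit missing-equals-failure and missing-equals-excluded analyses carry no on-treatment limit (7.2.2.1) and so do not depend on this date. The B/F/TAF phase is less exposed, because subjects who stop there do not continue scheduled visits (Protocol 6.5.1). All results are descriptive (SAP 3.5). The change is still worth making: the rule is wrong where it applies, and a near-exact bound is already in the visit schedule.

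**What to change.** In SAP 3.8.1 and Appendix 7 item 13, bound the imputed E/C/F/TAF date by the earliest available of:
- the ESDD visit date;
- the day before the start of any non-study antiretroviral;
- the end of the known year of last dose;
- a complete death date.

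If there is no ESDD visit, use the last dispensing date or the last visit at which the subject is known to have been on drug. Flag imputed dates in the exposure listing. Do not cap at a date from the Study Drug Completion eCRF unless that form is shown to record one; SAP 3.8.1 cites it only for discontinuation or completion status.

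The cost is a few sentences and minor programming on visit, dispensing, medication and death dates. An ESDD limit can still overstate exposure by up to 3 days. The dispensing-date fallback can understate it by up to one dispensing interval, which is 12 weeks at the later visits. If the SAP is already final, its introduction allows the change to be documented in the study report. If no subject meets the condition, one sentence saying so is enough.

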3.8.2. Analysis Windows

Subject visits might not occur on protocol-specified days. Therefore, for the purposes of analysis, observations will be assigned to analysis windows.

3.8.2.1. Analysis Windows for E/C/F/TAF Phase

The analysis windows for HIV-1 RNA, CD4 cell count, CD4%, hematology (excluding INR), chemistry, eGFR_{CG}, vital signs, weight, visual analogue scale (VAS), and healthcare utilization assessment are presented in [Table 3-1](#).

Table 3-1. Analysis Windows for HIV-1 RNA, CD4 Cell Count, CD4%, Hematology^a, Chemistry^b, eGFR_{CG}, Vital Signs, Weight, Visual Analogue Scale (VAS), and Healthcare Utilization Assessment (E/C/F/TAF Phase)

Visit ID	Nominal Day	Lower Limit	Upper Limit
Baseline			1
Week 2	14	2	21
Week 4	28	22	42
Week 8	56	43	70
Week 12	84	71	126
Week 24	168	127	210
Week 36	252	211	294
Week 48	336	295	378
Week 60	420	379	462
Week 72	504	463	546
Week 84	588	547	630
Week 96	672	631	714
Week 108	756	715	798
Week 120	840	799	882

a Hematology panel excluding INR and prothrombin time.

b Chemistry profile includes alkaline phosphatase, AST, ALT, GGT, total bilirubin, direct and indirect bilirubin, total protein, albumin, LDH, CPK, bicarbonate, BUN, calcium, chloride, creatinine, glucose, phosphorus, magnesium, potassium, sodium, uric acid, and amylase.

Note: The above analysis windows will also be used for bone biomarker of parathyroid hormone (PTH).

The analysis windows for fasting glucose and lipid panel (total cholesterol, HDL, direct LDL, triglycerides, and total cholesterol to HDL ratio) are presented in [Table 3-2](#).

Table 3-2. Analysis Windows for Fasting Glucose and Lipid Panel (E/C/F/TAF Phase)

Visit ID	Nominal Day	Lower Limit	Upper Limit
Baseline			1
Week 24	168	2	252
Week 48	336	253	420
Week 72	504	421	588
Week 96	672	589	756
Week 120	840	757	924

The analysis windows for prothrombin time and INR are presented in [Table 3-3](#).

Table 3-3. Analysis Windows for prothrombin time and INR (E/C/F/TAF Phase)

Visit ID	Nominal Day	Lower Limit	Upper Limit
Baseline			1
Week 24	168	2	252
Week 48	336	253	588
Week 120	840	589	1092

The analysis windows for SF-36 and HIV-TSQc are presented in [Table 3-4](#).

Table 3-4. Analysis Windows for SF-36 and HIV-TSQc (E/C/F/TAF Phase)

Visit ID	Nominal Day	Lower Limit	Upper Limit
Baseline ^a			1
Week 24	168	2	252
Week 48	336	253	420
Week 72	504	421	588
Week 96	672	589	756
Week 120	840	757	924

a HIV TSQc does not have a baseline assessment so analysis window at baseline does not apply.

The analysis windows for HIV-TSQs are presented in [Table 3-5](#).

Table 3-5. Analysis Windows for HIV-TSQs (E/C/F/TAF Phase)

Visit ID	Nominal Day	Lower Limit	Upper Limit
Baseline			1
Week 4	28	2	98
Week 24	168	99	252
Week 48	336	253	420
Week 72	504	421	588
Week 96	672	589	756
Week 120	840	757	924

The analysis windows for safety ECG are presented in [Table 3-6](#).

Table 3-6. Analysis Windows for Safety ECG (E/C/F/TAF Phase)

Visit ID	Nominal Day	Lower Limit	Upper Limit
Baseline			1
Week 48	336	2	504
Week 96	672	505	840

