6.4. Treatment Assessments (Post Week 96 until the Open-Label Rollover Extension)

6.4.1. Post Week 96 Assessments to End of E/C/F/TAF visit

After the Week 96 visit, subjects will continue to take their study drug and attend visits every 12 weeks until the End of E/C/F/TAF visit. Study visits are to be completed within \pm 6 days of the protocol-specified visit date unless otherwise specified.

Note: Regularly scheduled evaluations will be made on all subjects whether or not they continue to receive study drug.

- Review of AEs and changes in concomitant medications
- Symptom-directed physical examination as needed
- Vital signs (blood pressure, pulse, respiration rate, and temperature) and weight
- Blood sample collection for the following laboratory analyses:
 - Chemistry profile: alkaline phosphatase, AST, ALT, GGT, total bilirubin, direct and indirect bilirubin, total protein, albumin, LDH, CPK, bicarbonate, BUN, calcium, chloride, creatinine, glucose, phosphorus, magnesium, potassium, sodium, uric acid, PT/INR, amylase (reflex lipase testing is performed in subjects with total amylase $> 1.5 \times$ ULN) and PTH
 - Metabolic assessments: Fasting (no food or drinks, except water, at least 8 hours prior to blood collection) glucose and lipid panel (total cholesterol, HDL, direct LDL, and triglycerides). If the subject has not fasted prior to the visit, the visit may proceed, but the subject must return within 72 hours in a fasted state to draw blood for the metabolic assessments (**Every 24 weeks**)
 - Estimated glomerular filtration rate according to the Cockcroft-Gault formula for creatinine clearance
 - Hematology profile: complete blood count (CBC) with differential and platelet count
 - Plasma HIV-1 RNA (Taqman v2.0)
 - Subjects who meet the criteria for virologic rebound should be managed according to Management of Suspected Virologic Failure (Section [6.7.1](#)).
 - CD4+ T cell count
 - Plasma storage sample for virology, safety and/or PK testing

- Serum and plasma storage samples for possible additional clinical testing (for subjects who provide consent)
- Serum pregnancy test (females of childbearing potential only).
 - Serum pregnancy testing may be performed more frequently if required by local regulations.
- Study drug dispensation. Document study drug dispensation and accountability.

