6.4.2. End of E/C/F/TAF Visit

At Week 96 or the End of E/C/F/TAF Visit, subjects will discontinue E/C/F/TAF FDC and have the option to receive OL B/F/TAF FDC.

Subjects who complete the study through the End of E/C/F/TAF Visit and do not continue on the open label B/F/TAF FDC extension phase will be required to return to the clinic after the End of E/C/F/TAF visit for a 30-Day Follow-Up Visit.

Subjects who have discontinued drug study prior to the Week 96 or End of E/C/F/TAF Visit will not be eligible for the open-label rollover extension; these subjects will be asked to continue attending the scheduled study visits through the Week 96 Visit.

The following will be performed at the End of E/C/F/TAF Visit:

- Review of AEs and changes in concomitant medications
- Symptom-directed physical examination as needed
- Vital signs (blood pressure, pulse, respiration rate, and temperature) and weight
- 12 Lead ECG (performed supine)
- Blood sample collection for the following laboratory analyses:
 - Chemistry profile: alkaline phosphatase, AST, ALT, GGT, total bilirubin, direct and indirect bilirubin, total protein, albumin, LDH, CPK, bicarbonate, BUN, calcium, chloride, creatinine, glucose, phosphorus, magnesium, potassium, sodium, uric acid, PT/INR, amylase (reflex lipase testing is performed in subjects with total amylase $> 1.5 \times \text{ULN}$) and PTH

Note: At the End of E/C/F/TAF Visit, analyses of glucose will be done as part of the fasting metabolic assessments and not as part of the chemistry profile.

- This sample should be drawn prior to hemodialysis.
 - The timing of draw and timing of hemodialysis should be recorded.

- Metabolic assessments: Fasting (no food or drinks, except water, at least 8 hours prior to blood collection) glucose and lipid panel (total cholesterol, HDL, direct LDL, and triglycerides). If the subject has not fasted prior to the visit, the visit may proceed, but the subject must return within 72 hours in a fasted state to draw blood for the metabolic assessments
- Estimated glomerular filtration rate according to the Cockcroft-Gault formula for creatinine clearance
- Hematology profile: complete blood count (CBC) with differential and platelet count
- Plasma HIV-1 RNA (Taqman v2.0)
- Subjects who meet the criteria for virologic rebound should be managed according to Management of Suspected Virologic Failure (Section [6.7.1](#)).
- CD4+ T cell count
- Plasma storage sample for virology, safety and/or PK testing

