- For postbaseline visits, the most conservative value within the window will be selected for categorical observations other than patient reported outcomes (eg, abnormal will be selected over normal for safety ECG findings).
- For patient-reported outcomes collected at postbaseline visits, the record closest to the nominal day for that visit will be selected. If there are 2 records equidistant from the nominal day, the later will be selected.

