8.7. Electrocardiogram Results

A shift table of the investigators' assessment of ECG results at each scheduled postbaseline visit (Weeks 48 and 96 for the E/C/F/TAF Safety Analysis Set and Week 48 for the B/F/TAF Safety Analysis Set) compared with baseline values will be presented using the following categories: normal; abnormal, not clinically significant; abnormal, clinically significant; and missing. The number and percentage of subjects in each cross-classification group of the shift table will be presented. Subjects with a missing value at baseline or postbaseline will not be included in the denominator for percentage calculation. No inferential statistics will be provided.

A by-subject listing for ECG assessment results will be provided by subject ID number and visit in chronological order.

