- b) Last Study Date is the maximum of nonmissing study drug start dates and end dates, clinic visit and laboratory visit dates, including the 30-day follow-up visit date for subjects who prematurely discontinued study or who completed study according to study completion eCRF. Please note: if study drug start date or end date is partially missing, the imputed date (day imputed as 15) will be used. If subject died and the death date is complete (ie, not partial date) and before the imputed last study date, the complete death date should be used as the imputed last study date. Note that last visit date and last lab date include the 30-day follow-up visit.

14) Toxicity Grades:

- a) With regards to Triglycerides and Hypercholesterolemia, if the fasting status is not 'Y', in other words it is blank or 'N', then the lab result value would not be graded as non-fasting values are not interpretable.
- b) For toxicity grade summary, we will include all postbaseline graded results up to 30 days after the last dose of study drug, not just those at summarized visits.

15) Clarification of the following LOCF algorithms:

- Baseline values will not be carried forward.
- For CD4: If a value is missing in an analysis visit window, replace the missing value with the last on-treatment value observed before the analysis visit window that has the missing value.

16) For safety ECGs at postbaseline visits, the most conservative (worst) value within the window will be selected, eg, abnormal will be selected over normal for safety ECG or clinically significant abnormal will be selected over not clinically significant normal if there are multiple abnormal findings.

17) Treatment-Emergent Adverse Events

Events with Missing Onset Day and/or Month

The event is treatment emergent for the E/C/F/TAF phase if the following 3 criteria are met:

- The month and year (or year) of onset date is the same as or after the month and year (or year) of the first dose of E/C/F/TAF study drug, and
- The month and year (or year) of the onset date is the same as or before the month and year (or year) of the date corresponding to the minimum of (1) the last dose of E/C/F/TAF study drug plus 30 days AND (2) the first dose of B/F/TAF study drug minus 1 day, and
- End date is as follows:

The (complete) end date is on or after the first E/C/F/TAF dose date, or

The month and year (or year) of end date is the same or after the month and year (or year) of the first dose of E/C/F/TAF study drug, or

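### The End of E/C/F/TAF ECG has no analysis window of its own, so it can set the Week 96 category or drop out of the E/C/F/TAF shift table

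*SAP*

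**What the plan says.** Table 3-6 in SAP 3.8.2.1 ("Table 3-6. Analysis Windows for Safety ECG (E/C/F/TAF Phase") has a baseline row, a Week 48 row (nominal Day 336, Days 2 to 504) and a last row that reads "Week 96 672 505 840": visit, nominal day, lower limit, upper limit. No row follows it.

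For several records in one window, SAP 3.8.3 says that "the most conservative value within the window will be selected for categorical observations other than patient reported outcomes". Appendix 7 item 16 repeats this for ECGs: "For safety ECGs at postbaseline visits, the most conservative (worst) value within the window will be selected".

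Protocol 6.3 schedules ECGs at Weeks 48 and 96. Protocol 6.4.2 adds one at the End of E/C/F/TAF visit ("12 Lead ECG (performed supine"), and Appendix 2 agrees. Under Protocol 6.4.1, subjects who go on after Week 96 "attend visits every 12 weeks until the End of E/C/F/TAF visit". Neither document fixes a day for that visit.

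SAP 8.7 plans a shift table "at each scheduled postbaseline visit (Weeks 48 and 96 for the E/C/F/TAF Safety Analysis Set", with Week 48 alone for the B/F/TAF set, and a by-subject listing of ECG results. SAP sections 3 and 8 treat ECGs up to the first B/F/TAF dose date as E/C/F/TAF-phase data. SAP 3.8.1 takes the last value on or before that date as the B/F/TAF baseline.

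**The concern.** A scheduled safety assessment has no place of its own in the analysis, and where it ends up depends on its date.

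If the End visit is a separate visit held by Day 840, its ECG competes with the true Week 96 ECG under a rule that keeps the worse. A finding that first appeared weeks after Week 96 can then be tabulated as a Week 96 finding. Subjects with two ECGs in the window have two chances to be classed as abnormal, while those with one have one.

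If the End visit falls on Day 841 or later, its ECG is still E/C/F/TAF-phase data but has no window in that phase, so a worsening late in E/C/F/TAF treatment would not appear in the E/C/F/TAF shift table.

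This looks like an oversight. Tables 3-1 to 3-5 all carry a Week 120 row; only the ECG table does not. Protocol 8.5.4 calls for abnormal ECGs to be summarised by visit, and SAP 8.10 declares no change from the protocol's safety analyses.

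**Working it through.** **Reproducing the window.** Nominal days are 48 × 7 = 336 and 96 × 7 = 672. Half the gap is (672 − 336)/2 = 168. Week 48 therefore ends at 336 + 168 = 504, and Week 96 runs from 505 to 672 + 168 = 840. These are the limits in Table 3-6. The window closes 168 days after nominal Week 96 because no later target was entered.

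**Where an End-visit ECG would fall.** SAP 3.8.1 counts study day as visit date minus Study Day 1 plus 1, so week w falls on Study Day 7w + 1 if the first dose is taken on the Day 1 visit date. Protocol 6.4.1 allows ± 6 days, which gives 13 possible days. The weeks below are illustrative multiples of the 12-week schedule.

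| If the End visit is at | Study Day | Range | Days inside 505–840 |
|---|---|---|---|
| Week 108 | 757 | 751–763 | 13 of 13 |
| Week 120 | 841 | 835–847 | 6 of 13 |
| Week 132 | 925 | 919–931 | 0 of 13 |

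Counting without the plus one (nominal Day 840, range 834–846) puts 7 of 13 Week 120 days inside. On either count, a Week 120 visit is kept or lost by a few days of scheduling.

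**What the worst-value rule does.** SAP 8.7 has three non-missing categories: normal; abnormal, not clinically significant; abnormal, clinically significant. With both ECGs in the window there are 3 × 3 = 9 ordered pairs. The End-visit ECG changes the Week 96 category in the 3 pairs where it is worse; in the other 6 the Week 96 ECG's own category stands. If there is no Week 96 ECG and no other ECG in the window, the End-visit ECG becomes the Week 96 result. These are counts of combinations, not probabilities. They show only that the rule never moves a subject to a milder category than the Week 96 ECG's own.

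**What happens from Day 841.** Table 3-6 has no row, so the ECG cannot enter the E/C/F/TAF shift table. If the subject takes B/F/TAF and this is the last ECG on or before the first dose, it is the B/F/TAF baseline (SAP 3.8.1; Table 3-10). It appears in the listing in any case.

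**Choosing a cut-off.** Table 3-1 ends Week 96 at Day 714, which is 672 + 42 and so matches the ± 6 weeks that Protocol 6.3 allows. Table 3-6 runs 840 − 714 = 126 days, or 18 weeks, beyond that. Tables 3-2, 3-4 and 3-5 end Week 96 at Day 756, but that would leave 6 of the 13 possible Week 108 days (751–756) in the Week 96 window. Day 714 leaves none. Under the plus-one rule, a Week 96 visit on the last permitted day is Study Day 673 + 42 = 715, one day past the limit; Table 3-1 already has this edge.

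**The case against.** The strongest defence is that the window follows mechanically from midpoint rules and that worst-value selection is a prespecified, conservative choice for safety data. Any error overstates abnormality, in one descriptive table with no inferential statistics. The contrast between subjects with one ECG and those with two is also not purely rollover against non-rollover: early-discontinuation ECGs, and End-visit ECGs from subjects who then decline B/F/TAF, can share the window too. One ECG closing one phase and opening the next is unavoidable for anyone who switches at Week 96. All of this stands, and it limits the importance of the point. It does not explain why a scheduled ECG lacks a row when every other E/C/F/TAF window table extends to Week 120.

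Three stronger readings are tempting and are not supported:

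- A reader might infer that every later End-visit ECG is reported as the Week 96 result. It is so only when it is worse or is the only ECG in the window.
- A reader might infer that an ECG from Day 841 on is lost. It is listed, and for a subject who takes B/F/TAF it is normally that phase's baseline. Only its place in the E/C/F/TAF shift table goes.
- A reader might try to size the effect from the three subjects reported in Protocol 1.2.5 with clinically significant ECGs at Week 48, treating two ECGs as independent. That count is of subjects who moved from a milder baseline, not a per-ECG probability, and independence within one person some weeks apart is implausible.

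**Conclusion.** The point holds as a minor one. The mechanism is certain from the documents: the End-visit ECG has no row, it shares Days 505 to 840 with the Week 96 ECG if done by then, the worse value is kept, and later ECGs leave the E/C/F/TAF shift table.

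Its size cannot be given. The documents state neither when End visits took place nor how many subjects had a separate one. The Week 108 and Week 120 rows in Table 3-1 show that E/C/F/TAF visits after Week 96 were expected, but do not say how many included an End-visit ECG. Subjects whose Week 96 visit was also their End visit are unaffected. The direction is known: towards more abnormal Week 96 results while the ECG is in the window, and towards missing late E/C/F/TAF findings once it is outside. The primary endpoint and the virologic endpoints are not touched.

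**What to change.** - In Table 3-6, end the Week 96 window at Day 714, as in Table 3-1.
- Add an End of E/C/F/TAF row from Day 715, with an upper limit that holds every such visit; Day 1092, already used in Table 3-3, is one choice.
- In SAP 8.7, tabulate that row as its own shift-table block.
- State that a subject whose Week 96 visit is also the End visit contributes to the Week 96 row only.
- State how a Week 96 visit on Study Day 715, the last day of its allowance, is assigned; using its visit label would settle it.

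The cost is a few lines in the SAP and one small extra table block. No new data are needed, and the worst-value rule can stay as it is.
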